5.3.2 Capecitabine Dose Modifications

Capecitabine will be initiated at 750 mg/m^2 orally twice daily $\times 14$ days on a 28-day treatment cycle. Dose should be calculated as a total daily dose of 1500 mg/m^2 , then divided into two doses.

For all capecitabine dose modifications, if the protocol indicated that the dose should be reduced for subsequent administrations, a reduction of at least 500 mg (of the total daily dose) should be implemented even if the calculation including the dose reduction results in the same number of pills as was originally administered (example: if treated originally at 2500 mg daily, only 2000 mg daily may be administered if a dose reduction was called for).

5.3.2.1 Hematologic Toxicities

ANC (/mm ³)		Platelets (/mm ³)	Modification
< 1500/mm ³	and/or	< 100,000/mm ³	Hold until ANC \geq 1500/mm ³ and platelets are \geq 100,000/mm ³ , resume at 20% dose reduction
\geq 1500/mm ³	and	\geq 100,000/mm ³	No dose modification

Mucositis, Diarrhea and Esophagitis

**** Adequate medical management for these conditions should be implemented before a dose modification is made for one of these symptoms****

Grade	Toxicities/Symptoms	Modification
1	Mucositis, esophagitis, or diarrhea	No dose modification
2	Diarrhea	No dose modification
2	Mucositis, or esophagitis	Hold until \leq grade 1 and resume at 20% dose reduction
3	Diarrhea	Hold until \leq grade 1; resume at 20% dose reduction
3 or 4	Mucositis or esophagitis	Hold until \leq grade 1; resume at 20% dose reduction

Palmar-Plantar Erythrodysesthesia Syndrome (Hand and Foot Rash)

Grade	Modification
1	No dose modification
2	Hold until symptoms resolve to grade 0 or 1. Resume at 20% dose reduction.
\geq 3	Hold until symptoms resolve to grade 0 or 1. Resume at 20% dose reduction.

5.3.2.2 Hyperbilirubinemia

If grade 3 or 4 hyperbilirubinemia occurs that is thought to be related to capecitabine, capcitabine should be held until the bilirubin improves to \leq 3.0 x institutional ULN.

For grade 3 toxicity, resume capecitabine at 75% of the original starting dose for the first incident, 50% of the original starting dose for the second incident, and discontinue treatment permanently for the third incident. If the patient has already had a dose modification for another toxicity, the new dose level should be used as the baseline for making these adjustments.

For grade 4 toxicity, resume capecitabine at 50% of the original starting dose for the first incident and discontinue treatment permanently for any subsequent incident. If the

patient has already had a dose modification for another toxicity, the new dose level should be used as the baseline for making these adjustments.

5.3.2.3 Non-hematologic Toxicity

For other non-hematologic toxicities, dose reductions of capecitabine will be at the discretion of the investigator. A 20% dose reduction must be performed with each subsequent reduction. A maximum of 2 dose reductions can be performed.

5.3.3 Temozolomide Dose Modifications

- **Dose reductions:** For non-hematologic grade 3 and 4 AEs (except for nausea and vomiting as well as AEs unrelated to treatment) the dose should be reduced according to the Temozolomide Dose Level Table at the discretion of the investigator. Dose reductions for treatment day ANC and platelet counts should also be made according to the Dose Level Table below. Each dose reduction will be a 20% reduction from the prior level.
- **Discontinuation:** Also, except for nausea and vomiting, if any of the same non-hematologic grade 3 and 4 AEs that are at least possibly related to temozolomide recur after two reductions for that AE, then temozolomide will be stopped.

Temozolomide Dose Level Table	
Dose Level	Dose in mg/m ²
0	200
-1	160
-2	128

*Note this is a 20% dose reduction with each dose level.

5.3.3.1 Hematologic Toxicity

ANC (/mm ³)		Platelets (/mm ³)	% of Planned Temozolomide
≥ 1500/mm ³	and	≥ 100,000/mm ³	100%
750-1499/mm ³	or	50,000-99,999/mm ³	Hold*
< 750/mm ³	or	< 50,000/mm ³	Hold**

* Upon recovery to ANC ≥ 1,500/mm³ and platelets to ≥ 100,000/mm³, the dose level -1 will be administered (160 mg/m²). Discontinue temozolomide dose if patients do not recover within ≤ 3 weeks. If patient was already receiving Temozolomide at the -1 dose level, reduce to the -2 dose (128 mg/m²).

** Upon recovery to ANC ≥ 1,500/mm³ and platelets to ≥ 100,000/mm³, the dose level -2 will be administered (128 mg/m²). Discontinue dose if patients do not recover within ≤ 3

weeks. If patient was already receiving Temozolomide at the -2 dose level, temozolomide should be discontinued.

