5.3 Dose Modifications

5.3.1 General

Dose reductions will be based on current dose. If dose reduction is required, reduction is permanent. Missed doses will not be made up. No dose escalation is permitted for any of the study drugs.

Dose will be modified for all drugs if there is $\geq 10\%$ change in patient's weight while on study. For oral agents, particularly capecitabine, a new dose calculation may result in the same number of pills to be administered due to rounding issues.

Doses will be determined according to (1) non-hematologic AEs during the previous cycle, as well as (2) the lowest ANC and platelet counts during that cycle.

Patients may receive **a maximum of two** dose reductions per agent. If a third reduction is required, the patient should discontinue all protocol treatment. However, for Arm A, patients may discontinue one agent due to toxicity and continue the other on-study.

If different percentages of dose reductions for a specific drug are required because of two different types of toxicities, the greater percentage dose reduction should be undertaken.

AEs determined to be unrelated to study treatment will not require dose reduction.

NOTE: If patients have been off study treatment ≥ 4 weeks of next planned cycle start date, patients must discontinue protocol treatment.

NOTE: Starting cycles early is prohibited due to safety purposes.

All toxicity grades below are described using the NCI Common Terminology Criteria for Adverse Events (CTCAE) version 4.0.

All appropriate treatment areas should have access to a copy of the CTCAE version 4.0. A copy of the CTCAE version 4.0 can be downloaded from the CTEP website (<http://ctep.cancer.gov>).

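### The temozolomide rule for milder cytopenia has no branch for a patient already at dose level -2 and, read literally, raises that patient's dose by 25%

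*Combined protocol and SAP*

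**What the plan says.** The hematologic table in section 5.3.3.1 has two hold bands for temozolomide, each with its own footnote.

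- **Footnote \*, milder band** (ANC 750-1499 or platelets 50,000-99,999). On recovery, "the dose level -1 will be administered (160 mg/m²". One exception depends on the current level: "If patient was already receiving Temozolomide at the -1 dose level, reduce to the -2 dose (128 mg/m²". Temozolomide is also stopped if counts take more than 3 weeks to recover.
- **Footnote \*\*, severe band** (ANC below 750 or platelets below 50,000). On recovery the dose is level -2, with this branch: "If patient was already receiving Temozolomide at the -2 dose level, temozolomide should be discontinued".

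The parent section, 5.3.3, gives three levels (200, 160 and 128 mg/m²) and adds: "Each dose reduction will be a 20% reduction from the prior level". It ties count-driven changes to the same table: "Dose reductions for treatment day ANC and platelet counts should also be made according to the Dose Level Table below".

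Section 5.3.1 governs all agents. "Dose reductions will be based on current dose. If dose reduction is required, reduction is permanent". "No dose escalation is permitted for any of the study drugs". It sets a maximum of two "dose reductions per agent. If a third reduction is required, the patient should discontinue all protocol treatment", although an Arm A patient may stop one agent for toxicity and stay on the other.

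**The concern.** Footnote \* states a default dose and then one exception. A patient at level -2 does not meet the exception, so the default applies and the resumption dose is 160 mg/m². The result runs backwards: within one count band, a patient coming from 160 drops to 128, while a patient coming from 128 rises to 160.

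The footnote is the specific instruction a site will consult after holding temozolomide for low counts. For this patient its answer is a dose that the general section prohibits. The general section rules out 160 but does not say in so many words what to do instead. One site might follow the footnote, another might resume at 128, and a third might stop. Section 8.2.10 lists neutropenia and thrombocytopenia among the effects of temozolomide, so the situation is realistic.

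**Working it through.** **Inputs.** Starting dose 200 mg/m² daily on days 10-14, i.e. 5 days (5.1.1). Each step is 20% from the prior level, and the lowest level is -2 (5.3.3). Resumption doses come from 5.3.3.1. At most two reductions per agent, permanent, with no escalation (5.3.1). Daily cap 400 mg (5.1.1.1).

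**1. Reproduce the dose levels.** 200 × 0.8 = 160 and 160 × 0.8 = 128. Both match the table.

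**2. Read the footnotes literally for every case.**

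| Current dose (mg/m²) | Footnote \* (milder band) | Footnote \*\* (severe band) |
|---|---|---|
| 200 (level 0) | 160 (-20%) | 128 (-36%) |
| 160 (level -1) | 128 (-20%) | 128 (-20%) |
| 128 (level -2) | **160 (+25%)** | stop |

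The exceptional cell is 160/128 - 1 = +0.25. The other five are consistent with 5.3.1.

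**3. Derive the action for that cell.**

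- 128/200 = 0.64 = 0.8². With each reduction defined as 20% from the prior level, a patient at 128 has used two reductions, whether that level was reached in one step or two. Reductions remaining: 2 - 2 = 0.
- A further step would be 128 × 0.8 = 102.4 mg/m², which is not in the table.
- In the milder band, footnote \* prescribes a reduction at both levels where it gives a workable answer (200 to 160, 160 to 128). The same event at level -2 would call for a third reduction, and 5.3.1 makes that a discontinuation.
- Footnote \*\* stops temozolomide at level -2. The etoposide rule in 5.3.5.1, whose trigger (ANC below 1500 and/or platelets below 100,000) includes the milder counts, also discontinues at its level -2.

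**4. Size of the difference per 5-day course.** BSA 1.8 m² is an illustrative assumption; doses are before capsule rounding.

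| Action | mg/m² per course | mg per course at BSA 1.8 |
|---|---|---|
| Stop | 0 | 0 |
| Resume at 128 | 128 × 5 = 640 | 640 × 1.8 = 1,152 |
| Literal footnote \* | 160 × 5 = 800 | 800 × 1.8 = 1,440 |

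The daily cap begins to limit the 160 mg/m² dose at 400/160 = 2.5 m². At 2.83 m², the top of the capecitabine dosing table in 5.1.1.1, the current dose is 128 × 2.83 = 362.2 mg/day against 400 mg capped, an increase of 400/362.2 - 1 = 10%.

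**The case against.** **The harmful reading is already barred.** Section 5.3.1 forbids escalation, so a careful site would not give 160 mg/m². In context, the default sentence was probably written for a patient at level 0 and the next for a patient at level -1. This stands, and it is why the point is minor. It does not make the footnote right: its stated answer for this patient is a prohibited dose, and 5.3.1 leaves the replacement to be worked out.

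**Stopping is inferred.** No sentence says it for this count band, and the discontinuation bullet in 5.3.3 covers only non-hematologic events. Section 5.3.1 does not say outright that a single drop from 200 to 128 counts as two reductions. Resuming at 128 would break neither the permanence rule nor the ban on escalation. It is fair to call this an inference, but it is well supported. If the one-step drop were counted as a single reduction, the two-reduction limit would not strictly apply, yet the table would still have no lower level and footnote \*\* would still stop at -2.

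**The etoposide rule is not an exact parallel.** It allows resumption at full dose if counts recover within a week, a distinction footnote \* does not make. That is correct, so the etoposide rule is supporting evidence only.

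**Capecitabine may be affected too.** Under 5.3.2.1 the same counts hold capecitabine and reduce it by 20%. A patient who reached temozolomide level -2 through two hematologic events may therefore also be facing a third capecitabine reduction, with no agent left to continue. That may well happen, but capecitabine is governed by its own rule and by 5.3.1, so the temozolomide wording needed is the same.

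**Conclusion.** The concern holds and is minor. Footnote \* omits the patient already at level -2, and its literal result, 128 to 160 mg/m² (+25%, less above BSA 2.5 because of the cap), contradicts 5.3.1. The omission and the arithmetic are certain. That temozolomide should stop is a sound inference. It rests on reading 5.3.3 so that 128 mg/m² represents two reductions, and on footnote \* calling for a reduction at each such event.

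Only Arm A patients (about 40 of 80) can be affected, and of those only the ones at level -2 who then have a milder-band count and recover within 3 weeks. The documents give no rate for this. The consequence is a possible dosing error, or sites handling the same patient differently. Power, alpha and the primary analysis are unaffected.

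**What to change.** Add to the end of footnote \* in 5.3.3.1 the sentence that already closes footnote \*\*: "If patient was already receiving Temozolomide at the -2 dose level, temozolomide should be discontinued". No other text is needed: 5.3.1 already says when an Arm A patient may continue the other agent, and 5.3.2.1 already covers capecitabine for the same counts. The cost is one sentence in a protocol amendment, with no change to sample size, analysis or data collection.

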5.3.3.2 Non-hematologic Toxicity

For non-hematologic toxicities, dose reductions of temozolomide will be at the discretion of the investigator. Dose reductions must follow the **Temozolomide Dose Level Table** above. A maximum of 2 dose reductions can be performed. For patients with significant liver function abnormalities the benefits and risks of continuing treatment should be carefully considered.

5.3.4 Cisplatin or Carboplatin Dose Modifications

- **Dose reductions:** For non-hematologic grade 3 and 4 AEs (except for nausea and vomiting as well as AEs unrelated to treatment) the dose should be reduced according to the Cisplatin/Carboplatin Dose Level Table at the discretion of the investigator. Dose reductions for treatment day (or within 2 days of treatment) ANC and platelet counts should also be made according to the Dose Level Table below.

NOTE: The etoposide will be held if platinum is held until a decision is made to skip platinum for the current cycle so that all drugs are kept on the same schedule.

- **Discontinuation** Also, except for nausea and vomiting, if any of the same non-hematologic grade 3 and 4 AEs that are at least possibly related to platinum recur after two reductions for that AE, then platinum will be stopped.
- A patient's protocol treatment will be discontinued if more than 2 cumulative dose reductions are necessary or if patients are unable to restart platinum within 3 weeks of interruption. Dose reductions will be permanent. Missed doses will be made up once toxicity is resolved per guidelines below.
- All toxicity grades below are described using the NCI Common Terminology Criteria for Adverse Events (CTCAE) version 4.0.

Cisplatin Dose Level Table	
Dose Level	Dose in mg/m ² (days 1-3)
0	25
-1	20
-2	16

*Note this is a 20% dose reduction with each dose level.

Carboplatin Dose Level Table	
Dose Level	Dose in AUC (day 1)
0	5
-1	4

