5.1.2 Cisplatin (or Carboplatin) and Etoposide—Arm B

Cycle = 21 days (+/- 2 days)

CBC will be monitored prior to day 1 of drug administration.

Premedication with ondansetron (or other 5HT3 antagonist) and dexamethasone prior to each chemotherapy administration (days 1-3) is required. Additional antiemetics, analgesics and anxiolytics may be used per the discretion of the treating physician. Pre- and post-treatment hydration may be administered per institutional standards.

If the treating physician chooses to use Aprepitant, when given once daily for 14 days as a 100 mg capsule with an oral contraceptive containing 35 mcg of ethinyl estradiol and 1 mg of norethindrone, this decreased the AUC of ethinyl estradiol by 43% and decreased the AUC of norethindrone by 8%. Women of childbearing potential using pregnancy contraception that includes ethinyl estradiol should not receive Aprepitant for the treatment of nausea/delayed emesis. Patients may change to a different method of contraception if they wish to use Aprepitant.

- Cisplatin 25 mg/m² daily x 3 days (days 1-3) to be administered per institutional guidelines.

OR

- Carboplatin target AUC of 5 once on day 1 to be administered per institutional guidelines

AND

- Etoposide 100mg/m² daily x 3 days (days 1-3) to be administered per institutional guidelines.

Continue treatment until patient develops disease progression (as defined by Section [6.1.4](#)) or unacceptable toxicity.

NOTE: Treatment will be administered on an outpatient basis unless local institutional standard practice requires inpatient administration.

NOTE: CALVERT FORMULA FOR CARBOPLATIN DOSING:

Total Dose (mg) = (target AUC) x (GFR + 25)

For the purposes of this protocol, the GFR is considered to be equivalent to the creatinine clearance.

Round up any creatinine \leq 0.6 mg/dL, to 0.6 mg/dL

Glomerular Filtration Rate (GFR) Estimation: Calculated creatinine clearance of \geq 50 cc/min using the Cockcroft-Gault formula:

Males:
$$\frac{(140 - \text{Age in years}) \times \text{Actual Body Weight in kg}}{72 \times \text{Serum Creatinine (mg/dL)}}$$

Females: Estimated creatinine clearance for males x 0.85

With the Calvert formula, the total (final) dose of carboplatin is calculated in mg, not mg/m².

DO NOT exceed a dose of 150 mg per AUC or cap at 750 mg/AUC5.

NOTE: Choice of platinum agent will be per treating physician discretion. Once a platinum agent is picked, no changes are allowed.

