5.3.5.1 Hematologic Toxicity

ANC (/mm ³)		Platelets (/mm ³)	Modification
< 1500/mm ³	and/or	< 100,000/mm ³	Hold until ANC \geq 1500/mm ³ and platelets are \geq 100,000/mm ³ , resume at 20% dose reduction*
\geq 1500/mm ³	and	\geq 100,000/mm ³	No dose modification

*This table applies to day of treatment (or within 2 days of treatment) hematologic toxicities.

*If ANC and platelet count recover within one week, resume therapy at 100%. If greater than 7 days to recovery, upon recovery to ANC \geq 1,500/mm³ and platelets to \geq 100,000/mm³, the dose level -1 will be administered (80 mg/m²). Discontinue etoposide dose if patients do not recover within \leq 3 weeks. If patient was already receiving Etoposide at the -1 dose level, reduce to the -2 dose (64 mg/m²).

If already receiving treatment at the -1 dose level, upon recovery to ANC \geq 1,500/mm³ and platelets to \geq 100,000/mm³, the dose level -2 will be administered (64 mg/m²). Discontinue dose if patients do not recover within \leq 3 weeks. If patient was already receiving Etoposide at the -2 dose level, treatment should be discontinued.

Neutropenia or Febrile Neutropenia

For nadir neutropenia in the absence of fever or with fever that is successfully treated by oral antibiotics, there will be no dose adjustment. Filgrastim, sargramostim, or pegfilgrastim are allowed and should be administered according to ASCO guidelines (54). For treatment delays due to chemotherapy toxicities of more than 7 days, Etoposide should be dose-reduced according to the Etoposide Dose Level Table for all subsequent cycles of chemotherapy. For neutropenic fever (ANC < 500/mm³) and temperature $>$ 100.5F) requiring intravenous antibiotics, the doses of all chemotherapy drugs (cisplatin and etoposide) should be reduced by one dose level according to the Etoposide Dose Level Table and the Cisplatin Dose Level Table for the next cycle and all subsequent cycles. If counts to not recover within 4 weeks, discontinue all protocol therapy.

Thrombocytopenia

For grade 4 nadir platelet count decrease (thrombocytopenia) (platelets < 25,000/mm³), the dose of Etoposide should be reduced by one dose level according to the Etoposide Dose Level Table for the next cycle and for all subsequent cycles of chemotherapy. If counts do not recover within 4 weeks, discontinue all protocol therapy.

Anemia

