8.4.5 Dose Specifics

Carboplatin will be administered at AUC 5 IV on day 1 every 21 days (3 week cycles).

Calvert Formula for Carboplatin (AUC) Dosing

Total dose (mg) = target AUC (in mg/mL/minute) * GFR (in L/minute) + 25]

For the purposes of this protocol, the GFR is considered to be equivalent to the creatinine clearance.

Glomerular Filtration Rate (GFR) Estimation: Calculated creatinine clearance of \geq 50 cc/min using the Cockcroft-Gault formula:

Males:
$$\frac{(140 - \text{Age in years}) \times \text{Actual Body Weight in kg}}{72 \times \text{Serum Creatinine (mg/dL)}}$$

Females: Estimated creatinine clearance for males x 0.85

With the Calvert formula, the total (final) dose of carboplatin is calculated in mg, not mg/m².

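### Carboplatin dosing is wrong as printed in two places: a permitted second reduction has no dose level, and the Section 8.4.5 formula disagrees with Section 5.1.2

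*Combined protocol and SAP*

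**What the plan says.** **Reductions allowed.** Section 5.3.1 permits at most two reductions per agent and adds: "If a third reduction is required, the patient should discontinue all protocol treatment". For platinum, Section 5.3.4 repeats the limit: a patient's "protocol treatment will be discontinued if more than 2 cumulative dose reductions are necessary". It also says that if the same non-hematologic grade 3 or 4 events "recur after two reductions for that AE, then platinum will be stopped". That rule presupposes that two reductions can be made.

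**Levels printed.** The table headed "Carboplatin Dose Level Table" in Section 5.3.4 shows level 0 (AUC 5) and level -1 (AUC 4), and nothing further.

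**Formula.** Section 5.1.2 prints "Total Dose (mg) = (target AUC) x (GFR + 25", with the bracket closed straight after the 25. Section 8.4.5 prints "target AUC (in mg/mL/minute) * GFR (in L/minute) + 25", followed by a closing square bracket that has no opening partner. Both sections equate GFR with creatinine clearance and give that clearance in cc/min.

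**Limits.** Only Section 5.1.2 gives a dose cap (150 mg per unit of AUC, or 750 mg at AUC 5) and a creatinine floor (0.6 mg/dL). Section 8.4.5 mentions neither. A footnote to the study schema refers sites to Section 5.1.2 for the carboplatin dose.

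**The concern.** In Arm B the treating physician chooses the platinum agent, and no switch is allowed afterwards. A carboplatin patient who has a second qualifying toxicity is still within the permitted number of reductions, but the protocol gives no dose to move to. The site must then improvise a level, repeat AUC 4 or stop treatment, and different sites may do different things.

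The second fault concerns which section staff open. The drug-specific section, 8.4.5, does not print the same formula as the treatment section, and it lacks the limits given there. At stake are patient safety and consistent dosing in the control arm. The primary test and its operating characteristics are not involved.

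**Working it through.** **Reduction levels, side by side**

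| Agent (section) | Level 0 | Level -1 | Level -2 |
|---|---|---|---|
| Temozolomide (5.3.3), mg/m² | 200 | 160 | 128 |
| Cisplatin (5.3.4), mg/m² | 25 | 20 | 16 |
| Etoposide (5.3.5), mg/m² | 100 | 80 | 64 |
| Carboplatin (5.3.4), AUC | 5 | 4 | not printed |

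Reductions allowed: 2. Reduced levels printed for carboplatin: 1. One permitted reduction is therefore undefined.

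The gap can be reached under the protocol's own rules. In Section 5.3.4.1 the carboplatin column asks for a one-level reduction after grade 4 neutropenia and again after grade 2 thrombocytopenia. A patient who has one and then, in a later cycle, the other has had two reductions, which is not more than two, so treatment continues. The second step starts from AUC 4 and has no printed destination.

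**Formula.** Inputs: AUC 5 (5.1.2 and 8.4.5). GFR 100 mL/min = 0.1 L/min is an illustrative value that the documents do not give.

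1. The plan's own cap reproduces: 150 × 5 = 750 mg. Under 5.1.2 it is reached at GFR = 750/5 − 25 = 125 mL/min.
2. Section 5.1.2: 5 × (100 + 25) = 625 mg.
3. Section 8.4.5 with an opening bracket restored and GFR in mL/min: 5 × (100 + 25) = 625 mg, the same as 5.1.2.
4. Section 8.4.5 without the bracket and with GFR in mL/min: 5 × 100 + 25 = 525 mg, which is 100 mg lower.
5. Section 8.4.5 with the printed unit: 5 × (0.1 + 25) = 125.5 mg with the bracket restored, and 5 × 0.1 + 25 = 25.5 mg without it.

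Steps 3 and 5 show that the bracket and the unit are separate faults. A bracket lost in PDF reading would explain step 4, but not the L/minute unit. Step 5 is a test of the printed text, not a forecast of what anyone would give.

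**Limits missing from 8.4.5**

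- Cap: from GFR 50 to 125 mL/min the 5.1.2 formula gives 375 to 750 mg, so the cap changes nothing. At GFR 150 it gives 5 × (150 + 25) = 875 mg, against 750 mg with the cap, a difference of 125 mg.
- Cap and floor together, for an assumed man of 60 years and 70 kg with creatinine 0.5 mg/dL:
  - With the floor, clearance is (80 × 70)/(72 × 0.6) = 129.6 mL/min and the dose is 5 × (129.6 + 25) = 773 mg, capped at 750 mg.
  - With neither floor nor cap, clearance is (80 × 70)/(72 × 0.5) = 155.6 mL/min and the dose is 5 × (155.6 + 25) = 903 mg.

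**The case against.** **Lost text.** The other three dose-level tables end with a note on the 20% step; the carboplatin table has no such note. That is compatible with a row lost in PDF reading but does not prove it, since the source may simply lack the note. The caveat stands, and the source must be checked.

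**Discretion.** Two reductions is a ceiling, and Section 5.3.4.1 calls its rules general guidelines that leave room for investigator judgement. This softens the consequence but does not supply a dose. The recurrence rule in 5.3.4 still depends on a second reduction being possible.

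**Section 5.1.2 governs.** The schema footnote points there, and that section has matched brackets, the cap and the floor. This largely stands: 8.4.5 is a faulty duplicate, and sites do have a usable instruction.

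Four stronger readings are tempting, and the documents do not support them:

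- *That a site would give 25.5 or 125.5 mg.* This needs the L/minute unit to be taken literally, against the cc/min clearance in 8.4.5 itself and the pointer to 5.1.2.
- *That the limits contradict each other.* The two forms of the cap agree at AUC 5, and 8.4.5 states no rival figure. It is an omission.
- *That the renal thresholds conflict.* Clearance of at least 60 ml/min is an eligibility limit applied before randomization. The figure of at least 50 cc/min sits in the dosing calculation and is the same in 5.1.2 and 8.4.5. A patient can enter above 60 and later fall below it.
- *That carboplatin patients have no febrile neutropenia rule.* Section 5.3.5.1 does say "the doses of all chemotherapy drugs (cisplatin and etoposide) should be reduced by one dose level", which leaves carboplatin out. But 5.3.4.1 has a carboplatin column for that event, so only the wording needs tidying.

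**Conclusion.** Both faults hold on the text as printed. First, two carboplatin reductions are allowed and one reduced level is defined, so one permitted step has no stated dose. This is the firmer and more consequential fault, subject to checking the source table for a lost row. Second, the formula in 8.4.5 disagrees with 5.1.2 in bracket and unit and with its own section in unit, and 8.4.5 omits the cap and the creatinine floor.

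An omitted bracket alone changes the dose by 100 mg at AUC 5 (525 against 625 mg at GFR 100). The missing cap matters only above GFR 125 mL/min, by 125 mg at GFR 150. These figures rest on illustrative GFR values and on a reader using 8.4.5 alone.

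The documents do not say what share of the 39 eligible patients planned per arm would receive carboplatin or need a second reduction. The effect on control-arm dose intensity therefore cannot be quantified. Sample size, power and alpha are unaffected.

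**What to change.** 1. Check the carboplatin dose level table against the source document.
2. If no row was lost, the clinical team should reconcile the number of carboplatin levels with the number of reductions allowed in 5.3.1 and 5.3.4. Which of the two changes, and to what, is a clinical decision.
3. Make 5.1.2 and 8.4.5 agree on formula, units, cap and creatinine floor, or replace the text in 8.4.5 with a cross-reference to 5.1.2 once the clinical team has confirmed the content.
4. As wording clean-up only, say how the sentence in 5.3.5.1 that names cisplatin and etoposide relates to the carboplatin febrile neutropenia rule in 5.3.4.1.

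The cost is a wording amendment and its circulation to sites. No data collection, analysis or sample size changes.
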